6. PARTICIPANTS

A. TARGET POPULATION

Our target enrollment is 80 participants who complete all study procedures. However, we will recruit 4,000 participants between the ages of 18 and 65 to account for dropouts and ineligible participants. We have chosen to study adult daily smokers who have had a panic attack within the past year and use nicotine to regulate their emotions. Although subjects will be excluded at intake for use of certain psychotropic medications, we believe it would be unethical to prevent them from starting these medications once the study has begun. Thus, we will assess for the initiation of psychotropic medications throughout treatment and utilize this information when analyzing the study results. Participants evidencing suicidal ideation at screening will be referred to treatment and excluded from the study.

Inclusion of Women and Minorities

Those who do not have adequate command of the English language will not be included in the study. All materials for the study including the measures are written in English and developing psychometrics for non-English speaking populations is beyond the scope of this project. If eligible, participants will be enrolled without regard to ethnic background. To increase minority participation, we will utilize a multimedia campaign with the following strategies: flyers in information booths at community and church functions, and placement of flyers in retail outlets and organizations known to serve minorities. We will use the aforementioned recruitment strategies in a sustained manner in the hope of boosting minority enrollment to 40%; we have achieved this level of minority recruitment in recent studies using these methods (Hofmann, Meuret, Smits et al., 2006; [name], Feldner et al., 2005).

Inclusion of Children

Participants below the age of 18 (and adults above 65 years old) will not be included in the proposed research

study for several reasons. First, the study hypotheses are not directly relevant to children or older adults without significant modification to take into account differing cognitive and developmental issues as well as issues related to smoking metabolism. These different issues could manifest in behavior, affect, psychophysiology, and/or neurobiology. If children and older adults were to be included, the study design would, at a minimum, have to take these factors into account and hypotheses would have to be added. To do so, the sample size would have to be increased considerably to yield adequate power to test these additional hypotheses. The budget allocation for an individual project simply does not allow for this possibility without seriously compromising other aspects of the study. Second, we elected not to include individuals below the age of 18 for two significant reasons. One reason is that individuals below the age of 18 experience markedly lower rates of smoking and anxiety-related problems than do adults (Fiore et al., 2000, 2008; Ollendick, Mattis, & King, 1994). Given these findings, it is most parsimonious to sample adults at this stage of treatment development. A second reason is that it has been repeatedly hypothesized that panic problems are rare among children due to their limited cognitive capacities (Nelles & Barlow, 1988; Vasey & Daleiden, 1994). Specifically, youths have a limited ability to attribute anxiety to internal cues or associating the sensations of anxiety with mental or physical catastrophe, a process central to the AS construct. Thus, restricting this initial investigation of AS and smoking to adult participants will help eliminate concerns regarding the cognitive capacities of children. Additionally, if children were to be included, the study design would, at a minimum, have to take these factors into account and additional hypotheses would need to be added. To do so, the sample size would have to be increased considerably to provide for adequate power to test these new hypotheses. Therefore, to focus on individuals below the age of 18 years does not make practical or clinical sense or offer help in developing more generalizable data.

B. INCLUSION/EXCLUSION

Inclusion Criteria:

- Male and female patients ages 18-65 capable of providing informed consent
- Willing and able to provide informed consent, attend all study visits and comply with the protocol
- Daily smoker for at least one year
- Currently smoke an average of at least 8 cigarettes per day
- Report a motivation to quit smoking in the next month of at least 5 on a 10-point scale
- Evidence of panic attack within the past year and endorsement of smoking as an emotion regulation strategy (i.e., score at least a 78 on the SAEQ).

Exclusion Criteria:

- Subjects who do not use smoking as an emotion regulation strategy
- Current diagnosis of a psychotic, eating, developmental or bipolar disorder
- Significant suicide risk as determined by structured interview
- Pregnant women, lactating women, and women of childbearing potential who are not using medically accepted

Research Proposal

forms of contraception (e.g., IUD, oral contraceptives, barrier devices, condoms and foam, or implanted progesterone rods stabilized for at least 3 months).

- Psychoactive substance abuse or dependence (excluding nicotine dependence) within the past 6 months
- Current use of isoniazid or ethionamide compounds
- A history of significant medical condition and/or be deemed as currently unhealthy by the study physician
- Limited mental competency and the inability to give informed, voluntary, written consent to participate
- Current use of any pharmacotherapy or psychotherapy for smoking cessation not provided by the researchers during the quit attempt
- Concurrent psychotherapy initiated within three months of baseline, or ongoing psychotherapy of any duration directed specifically toward treatment of anxiety or mood disorder other than general supportive therapy initiated at least 3 months prior to the study
- Use of other tobacco products
- Plans to move outside of the immediate area in the next six months
- Insufficient command of the English language

C. BENEFITS

Participants will have opportunity for direct benefit in the care and treatment of cigarette smoking. The population of adult smokers in general has a great opportunity for benefit since the results of the study may be valuable in the treatment of smoking. If we find that DCS augments PSRT, then smokers could elect this augmentation strategy to improve their quality of life. Further, the proposed study (i.e., design, assessment schedule, and analyses) offers the potential to improve the understanding of the mechanisms that underlie these effects. Thus, the anticipated benefits of the study are twofold: the results will be used to advance understanding of the factors related to anxiety and relapse to smoking after attempts at smoking cessation, and significant knowledge about the combined effects of cognitive-behavioral treatment for anxiety related vulnerabilities and the nicotine patch will be obtained. Participants can potentially benefit from the smoking cessation and panic reduction treatment provided as part of the study. The results of the study will have implications for matching treatments to specific characteristics of smokers.

D. RISKS

The risks associated with participating in this study are minimal. Potential risks also include nicotine patch side effects. Common side effects include local skin irritation at the site of the patch, and mild nausea if the participant continues to smoke at a high level while using the patch, and temporary vivid dreams. Less common are allergic skin reactions.

The possible side effects for d-cycloserine include: headache, confusion, tremor, vertigo, memory difficulties, paresthesias (itching or tingling of the skin), seizure, drowsiness, confusion, dizziness, drowsiness, irritability, restlessness, depression, muscle twitching, trembling, nervousness, and speech problems. However, these side effects are most commonly related with doses greater than 500mg/day (i.e., chronic dosing), which is two times the amount that participants will receive in this study. DCS is a safe medication in the dosage provided; indeed

Research Proposal

10-fold doses are safely administered in chronic doses in other applications. Participants will be asked not to use any alcohol prior to the sessions and prior to the assessments. They will also be asked to breathe into a tube so that members of the study team can perform a test for the presence of alcohol. It should be noted that patients have been given acute 250mg doses in a previous study of obsessive compulsive disorder and 1000mg doses in a previous study of depression, with no significant adverse side effects associated with the administration in either study (Heresco-Levy et al., 2013; Storch et al., 2007). This dose of 250mg was selected for the current study as accumulating evidence suggests that a dose of 250mg may be more likely than a lower dose to aid the type of therapeutic learning that is the focus of the smoking cessation intervention that we will employ in this protocol.

Other potential risks include temporary nicotine withdrawal symptoms after quitting. Discomfort related to smoking cessation may include such symptoms as increased anxiety, irritability, difficulty concentrating, headaches, nausea, decreased heart rate, fatigue, increased hunger, and tobacco cravings. These symptoms are typical of nicotine withdrawal and result from the addictive nature of nicotine. Although symptoms of nicotine withdrawal may be uncomfortable, they are not harmful. It should be noted that participants in this study have already had numerous experiences with these sensations and feelings throughout their day-to-day life.

There are no absolute contraindications to the use of d-cycloserine in combination with other antibiotics. There are potential interactions with isoniazid and ethionamide compounds; current use of isoniazid or ethionamide compounds is listed as an exclusion criterion (see page 17).

The nicotine withdrawal state is primarily mediated by central and peripheral nicotinic acetylcholine activity. In rodent models, d-cycloserine has been shown to decrease nicotine self-administration therefore suggesting it may have an ameliorative effect on craving and withdrawal states. As an NMDA partial agonist, it is unlikely it will exacerbate nicotine withdrawal and there is no animal or human evidence it would exacerbate nicotine withdrawal.

There are no known risks associated with saliva cotinine and carbon monoxide analyses. The procedures for obtaining these samples are brief, safe, and minimally uncomfortable. Some participants may experience minor, short-term discomfort with these procedures. For example, some individuals may find it slightly uncomfortable to hold their breath for 15 seconds, as required for the carbon monoxide analysis. In addition, some individuals may report brief dry mouth following the saliva cotinine procedure.

The exposure-based treatment offered may make some patients anxious during the exposure procedures, but these procedures are generally very well accepted and are associated with treatment benefit (Gould et al., 1997). The assessment instruments may cause mild distress because of their focus on emotional topics associated with mental health.

Protection of Human Subjects from Research Risk

Adequacy of Protection Against Risks

The therapists are advanced doctoral students who are trained to identify a panic attack, and to help the patient recover. Specifically, the therapist will remind the patient that he/she is experiencing a false alarm, instruct the patient to breathe through the nose in order to reduce hyperventilation, and encourage the patient to allow the panic attack to run its course. Immediately following a panic attack, the therapist and patient will discuss the panic attack experience. This discussion is aimed to help the patient correct false beliefs regarding the consequences of panic attacks. The PI, [name]., is available for intervention as needed and back-up plans are established including involvement of the study physicians and referral to a hospital emergency department. These safety procedures have been effective in dealing with adverse physical and mental health events in previous and ongoing studies. Upon study completion, all participants will be referred to follow-up care if needed.

If the person is in imminent danger of harming him/herself, the interview will be stopped and 911 will be called. If the person is not in imminent danger, but seems to be in need of psychological services for suicidality, they will be encouraged to call the counseling center if he/she is a student or a local community agency if he/she is a community participant, to set up an appointment. The interviewer will make one follow-up call to the participant in the week following the assessment to ascertain whether he/she made the appointment and to get the name of the counselor he/she has been assigned to in order to inform the counselor of the participant's suicidality. If the participant decides not to make an appointment, no further action will be taken by [name]. If the participant makes the appointment and gives the name of the counselor, [name] will call the counselor within 24 hours to inform the counselor of the participant's suicidality (accompanied by the release of information form). If the participant is currently in therapy, [name] will call his/her therapist within 24 hours of the assessment if possible (accompanied by a release of information form) in order to inform the therapist of the participant's suicidality.

To minimize skin reactions due to nicotine patch, smokers will be instructed to move the site of patch placement each day and not repeat site use for at least one week. Smokers who smoke 4 cigs/day for 4 days will be asked to discontinue the patch until they are able to cut down or quit smoking again. The initial mg/day dose may be adjusted downward to 14 mg or 7 mg if there is significant nausea or other adverse reactions. Smokers will be instructed to remove the patch before bed if it significantly interferes with sleep. The patch will be discontinued entirely if severe skin reactions develop. Additionally, at each visit, participants will be administered a side effect and symptom profile. The most common side effects from using the nicotine patch are local skin irritation, nausea if the dose is too high (or if the patient continues to smoke at a high level while using the nicotine patch), and disturbed sleep and vivid dreams. Instructing the participant to rotate the site where the patch is applied and to remove the patch at night if sleep disturbance is impairing function will minimize these side effects. Participants will indicate on a checklist their incidence and severity of side effects. Checklists will be reviewed each visit by study personnel, and participants who report significant symptoms or adverse reactions will be interviewed separately to determine whether the patch should be discontinued or the dose reduced. Likewise, study staff will be available at all times to answer questions and concerns regarding symptoms. Participants who

discontinue the patch or change the assigned dose will be kept in the remaining treatment. We will track such changes to determine whether they affect outcomes. As noted in our previous trials, we have had little to no emergence of side effects with the patch ([name] et al., 2008). Nonetheless, we will specifically query for potential side effects at each visit.

In regard to withdrawal symptoms, there is a strong likelihood that most study participants will experience some nicotine withdrawal symptoms, including anxiety, restlessness, anger, irritability, sadness, problems concentrating, appetite change and weight gain, insomnia, and decreased heart rate. Because all participants will use the nicotine patch, this should diminish the overall severity of withdrawal discomfort, although the patch will not necessarily eliminate withdrawal discomfort entirely. Moreover, withdrawal symptoms are usually short-lived, with most symptoms abating within 1-2 weeks. During treatment, research team staff will monitor patients for development of severe psychological problems (e.g., depression) during each of our sessions and follow-up visits. Using the study instruments and clinical interviews, therapists will determine whether treatment or additional treatment for a specific psychological problem is needed and work with the patient to refer them to appropriate service centers.

Regarding the administration of DCS, the prescribing psychiatrist will be [name]., M.P.H., F.A.S.A.M. [name] will review the medical history of patients (for exclusion factors), and will prescribe the three doses of study medication (DCS vs. PBO) to be taken during assessment weeks (weeks 3-5). Patients will be encouraged to call the study physician should they experience any side effects or have any questions regarding the medication.

To deal with the potential risk of loss of privacy (judged to be minimal), we will maintain confidentiality by numerically coding all data, by disguising identifying information, and by keeping all data in locked file drawers. Video recordings will be coded by participant ID and will be deleted after therapist adherence ratings. Participant information will be accessible only to research staff. Identifying information will not be reported.

Functions of the Data and Safety Monitoring Board (DSMB)

A Data and Safety Monitoring Board (DSMB) will be created as an independent body charged with ensuring that the safety of study subjects is protected and that the scientific goals of the study are being met. To support those purposes, the DSMB will review any proposed amendments to the study protocol, perform expedited monitoring of all serious adverse events, perform ongoing monitoring of drop-outs and non-serious adverse events, determine whether study procedures should be changed or the study should be halted for reasons related to the safety of study subjects, and perform periodic review of the completeness and validity of data to be used for analysis of safety and efficacy. The DSMB will also ensure subject privacy and research data confidentiality. Members of the DSMB include the PI ([name].), the Co-PIs ([name]., and [name].); [name]. (Chair), [name].; [name].; and [name].

As in any clinical trial, it is not possible to anticipate all possible adverse events. We do extensive training with our staff on ascertaining, monitoring, and documenting adverse events. The study investigators have extensive experience in clinical trials organization and management, including data safety monitoring for single site and multi-site trials. We have established procedures for rendering first aid and life threatening emergencies. [name] will oversee these procedures.

Reporting Mechanisms of AEs/SAEs to the IRB and NIDA

Unblinded Reporting. Safety information for this study will be reported to the DSMB in an unblinded manner. A statistical penalty will not be assessed for the ongoing unblinded review of safety by the DSMB. Unblinded data will not be released to the investigators unless necessary for safety reasons.

Range of Safety Reporting to the DSMB. It is considered necessary for the purpose of monitoring the safety of the study that the DSMB review not only adverse events (AEs) and serious adverse events (SAEs), but other data that may reflect differences in safety between treatment groups. This includes treatment retention rates, and reasons for drop-out.

Serious Adverse Events. Expedited review will occur for all events meeting the FDA definition of Serious Adverse Events (SAEs) – i.e., any fatal event, immediately life-threatening event, permanently or substantially disabling event, event requiring or prolonging inpatient hospitalization, or any congenital anomaly. This also includes any event that a study investigator or the DSMB judges to impose a significant hazard, contraindication, side effect, or precaution. *For purposes of this study, all SAEs will be required to be reported to the DSMB, regardless of any judgment of their relatedness to the study treatment.* All relevant information will be reported to the DSMB for each SAE including information about the event and its outcome, concomitant medications, the subject's medical history and current conditions, and all relevant laboratory data. Notification by e-mail, and FAX transmittal of all related study forms shall be made to the DSMB within 2 days of the occurrence of any SAE. Information will be reviewed and a determination made of whether there was any possible relevance to the study. Additional reporting to the IRBs will be done within 24 hours of the SAE; reporting to NIDA will be made according to the regulations governing SAE reporting.

Non-Serious Adverse Events. At periodic intervals, the DSMB will be provided with unblinded summaries of the numbers and rates of adverse events by treatment group. These reports will include types of events, severity, and treatment phase. Data on individual non-serious adverse events is not expected to be needed for this review.

Other Safety-Related Reports. Throughout the course of the study, the DSMB will receive unblinded summary reports of treatment retention and reasons for drop-out.

Collection and Reporting of AEs and SAEs

Research Proposal

Information regarding AEs is to be obtained by questioning or examining the subject. At each visit all new complaints and symptoms (i.e., those not existing prior to signing of informed consent) must be recorded on the AE Form. Pre-existing complaints or symptoms that increased in intensity or frequency after having signed the Informed Consent Form must be entered on the AE Form also. All AEs must be characterized in terms of their start and stop dates, start and stop times, intensity, action taken on Intervention, relationship to Intervention, subject outcome and whether or not the AE led to a Serious Adverse Event (SAE). Any clinically relevant increase or decrease to the intensity or frequency of a reported AE requires a separate entry on the AE Form. If the event meets the definition of an SAE, the procedure for reporting SAEs must be followed; the event should not be reported on the AE Form also in case the start and stop dates are equal to the start and stop dates of the SAE.

A Serious Adverse Event (SAE) is defined as any untoward medical occurrence that:

- Results in death;
- Is life-threatening;
- Requires in-patient hospitalization or prolongation of existing hospitalization;
- Results in persistent or significant disability/incapacity; or
- Is a congenital anomaly/birth defect.

Medical and scientific judgment should be exercised in deciding whether expedited reporting is appropriate in other situations, such as important medical events that may not be immediately life-threatening or result in death or hospitalization, but may jeopardize the patient or may require intervention to prevent one of the other outcomes listed in the definition above. These should also usually be considered serious too.

All serious events occurring between signing of the Informed Consent Form by the subject and signing of the End of Trial Form by the investigator, except those pre-specified in the protocol, must be reported as soon as practical (within 24 hours of awareness) to the IRB and the DSMB. This includes serious events, which could be associated with the trial procedures, even if occurring outside the treatment period.

Follow-up of SAEs, which occurred during the trial, should in principle take place until resolution of the SAE. Under this protocol, the following event(s) will not be considered as (an) SAE(s) and should not be entered on the SAE form:

- Pre-planned hospitalizations for diagnostic, therapeutic, or surgical procedures for a pre-existing condition that did not worsen during the course of a clinical trial. These pre-planned hospitalizations must be entered on the medical history form, including the condition requiring hospitalization.
- Hospitalizations for uncomplicated delivery.

All SAEs (i.e. including serious events occurring outside the treatment period) must be reported as soon as practical (within 24 hours of awareness) to the IRB and DSMB. Reporting of an SAE must be done by means of

the SAE form. For each SAE, the investigator fills out this SAE form (as complete as possible) and sends the form and all available supporting documentation by fax.

Suicidality Plan

Endorsement of suicidal ideation will be assessed for level of risk. Low risk ideation (i.e. have thoughts or wishes to be dead with no plan or intent to hurt themselves) will be assessed at every session for changes to the risk level. Those with high risk ideation (i.e. has a plan and date in mind) will be sent a referral list that includes a 24/7 national hotline that they can call if necessary. Research personnel will communicate with the PI right away for supervision and will assess for appropriate procedures as necessary. Procedures include referral to counsellors, plans to get them to the hospital, and/or calling the police.

E. RECRUITMENT

Subjects will be recruited from the community and from physician referrals. Any subjects meeting the entrance inclusion criteria will be provided the opportunity to participate in this study. Recruitment sources include: 1) posting newspaper and Craigslist advertisements; 2) utilizing fliers, pamphlets, and handouts in community-based organizations, bulletin boards, stores, and handing them out at events and various other sites; 3) utilizing social media sites (e.g., Facebook, Twitter, LinkedIn) to post status updates with links to our online prescreen; 4) utilizing ResearchMatch; and 5) seeking organizations (eg. Live Tobacco Free Austin). It is noteworthy that these recruitment strategies have been, and are currently being, used to recruit smokers from the community for previous studies run in the Anxiety and Health Research Laboratory at the University of Houston (PI: [name]) and have been used effectively at the Anxiety Research and Treatment Program at Southern Methodist University (PI: [name]).

F. OBTAINING INFORMED CONSENT

Any subjects meeting the entrance inclusion criteria will be provided the opportunity to participate in this study. The consent form will be sent to participants via REDCap before the baseline appointment so that they have time to read through the form and give their informed consent. If a participant has not yet signed the consent form before the baseline session, we will give them the consent form to read over and sign. Research associates obtaining consent will explain the study procedures and answer any questions the potential participant might have. Informed consent will be obtained from all participants prior to undergoing any screening procedures. Participants may be asked to give signed consent on an electronic device such as an iPad using REDCap. Participants will read the consent form on the device, print their name, and sign using their finger or stylus directly onto the iPad. We will either provide them with a paper copy, or email them a copy of the consent form

for their records, depending on their preference. All paper consent forms will be kept in locked cabinets with ID numbers to assure each participant has signed a consent form for at least 3 years. All electronic consent forms will be housed in REDCap, which will be password protected and only accessible by the PI and study personnel. The Institutional Review Board at the University of Texas (UT) consists of independent bodies of reviewers. Research associates and physicians will receive training regarding procedures required to obtain informed consent, and training is completed yearly in order to continually reinforce such procedures.

The Prescreen Survey informed consent will detail procedures about the prescreen survey and screening assessment. Participants will read and give informed consent by clicking "I Agree" before continuing on with the survey. A waiver of documentation is requested for the prescreen survey informed consent procedures. All eligible participants will give signed, informed consent for the rest of the study procedures once they come into the lab for their first visit.

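### The DSMB is called independent but seats the PI and two Co-PIs and receives unblinded safety reports, against the protocol's own rule on releasing unblinded data to investigators

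*Protocol*

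**What the plan says.** All but one of the relevant statements are in Protocol section 6.D (Risks).

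- **Status.** Under *Functions of the Data and Safety Monitoring Board*, the DSMB "will be created as an independent body charged with ensuring that the safety of study subjects is protected".
- **Membership.** Later in that paragraph: "Members of the DSMB include the PI". Two Co-PIs follow, then a chair and three others. Names are masked, but the roles of PI and Co-PI are printed.
- **Duties.** "the DSMB will review any proposed amendments to the study protocol". On safety grounds the board also decides on procedural changes and on stopping the trial. A further duty is to "perform periodic review of the completeness and validity of data to be used for analysis of safety and efficacy".
- **Form of reports.** Under *Unblinded Reporting*: "Safety information for this study will be reported to the DSMB in an unblinded manner".
- **Release rule.** Same paragraph: "Unblinded data will not be released to the investigators unless necessary for safety reasons".
- **Routine content.** *Non-Serious Adverse Events* provides periodic unblinded summaries of event numbers and rates by arm. *Other Safety-Related Reports* provides unblinded retention and drop-out summaries for the duration of the study. *Serious Adverse Events* adds case-level material: "All relevant information will be reported to the DSMB for each SAE including information about the event and its outcome".

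Outside section 6.D, the *Randomization* part of section 4 states that participants and study personnel are both blinded to condition.

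**The concern.** A board that sees unblinded data is normally kept apart from the people running the trial, so that what it learns cannot influence how the trial is run. Here the same people sit on both sides. Read as written, the PI and Co-PIs receive as board members what the release rule withholds from them as investigators.

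The exposure matters because of what these people do. The PI reviews adverse-event forms at each visit (section 5, *Safety Monitoring and Concerns*). Each adverse event is rated for its relationship to the intervention (section 6.D, *Collection and Reporting of AEs and SAEs*). After an SAE reaches the DSMB, someone decides whether it may be relevant to the study; the text does not say who. Board members also review amendments, decide on safety-related changes or halting, and review the validity of the safety and efficacy data. The PI and Co-PIs would do all this for their own trial while holding unblinded safety information. The risk is bias in attribution and conduct, and a claim of blinding and independent monitoring that the text does not support.

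**Working it through.** No figure in the plan has to be reproduced. The check is whether the statements can all hold together.

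**Step 1: who is on the board.** Listed members: 1 PI + 2 Co-PIs + 1 chair + 3 others = 7. Investigators: 3/7 = 42.9%. Without them, 7 − 3 = 4 remain. Whether those four have a trial role cannot be judged, because names are masked.

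**Step 2: what the board receives.** Three streams fall under the general sentence on unblinded reporting.

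| Stream | Level | Basis for calling it unblinded |
|---|---|---|
| Non-serious adverse events | Group summary, periodic | Explicitly unblinded and by arm |
| Retention and drop-out | Group summary, ongoing | Called unblinded; does not say by arm |
| SAEs | Individual subject | General sentence only |

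**Step 3: put membership and reports together.** The PI and Co-PIs are DSMB members. The DSMB receives these reports. No text limits which members receive them. So the PI and Co-PIs receive them.

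**Step 4: test against the release rule.** The rule bars release to investigators, with one exception for safety need. The two group-summary streams are scheduled and go to the board whether or not a safety need has arisen. If a scheduled report counted as release needed for safety, the rule would bar nothing. The exception therefore does not reconcile the text.

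**Step 5: test against the blinding statement.** Section 4 says study personnel are blinded. By-arm summaries give investigators comparative information but do not hand over the allocation key, so they do not contradict the further statement that one named person alone can break the blind. SAE material would be the most direct breach of the personnel blind, provided it is unblinded as the general sentence says.

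**Step 6: how much time was left.** The SAP header date, read as 7 June 2017, to the planned end of data collection in section 4.C, taken as 31 August 2017: 23 + 31 + 31 = 85 days. A roster change made at or after the SAP date could affect at most 85 days of planned collection.

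**The case against.** The best case for the plan is that the text is incomplete, not contradictory. It says reports go to the DSMB without describing distribution inside the board, and the release rule could be read as a limit on members who are also investigators. A charter, not among these documents, might provide for closed sessions. The protocol also says the board's review of adverse events, retention and drop-out is considered necessary for monitoring safety, which might bring routine reports within the exception. These readings do not succeed. Nothing in the protocol limits distribution within the board, and the sentence on necessity concerns review by the DSMB, not release to investigators. An unseen charter could show what was done, but it would not make the protocol's own statements agree.

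Other objections stand as limits:

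- The listed contents of an SAE report do not include treatment assignment, and the investigator completes the SAE form anyway. Unblinding by that route rests on the general sentence alone.
- Individual non-serious event data are not expected to be needed, so the routine adverse-event reports are group summaries.
- The one decision explicitly tied to the PI's review of forms concerns the nicotine patch, which everyone receives. The rater of relationship to the intervention is not named, and no text has a Co-PI rating events.
- No by-arm efficacy report is listed, and reported abstinence is verified biochemically.
- The member list is introduced by a word that need not be exhaustive, so 3 of 7 describes the listed members only.

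These points hold down the severity. They do not remove the conflict between membership and the release rule.

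**Conclusion.** The concern holds. Following the protocol as written gives three investigators unblinded safety reports that the same section says investigators will not receive, and a board with 3 of 7 listed members from the trial's own leadership is not independent in the sense claimed. This should be fixed; it does not undermine the primary analysis.

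The conclusion assumes that reports to the DSMB go to all its members, as nothing says otherwise, and that the safety exception does not extend to scheduled reports. The size of any bias cannot be computed from the documents. They do not show that any bias occurred, and they do not show an effect on abstinence, lapse or relapse. With at most 85 days of planned data collection left at the SAP date, a late roster change would prevent little. The main remaining value is consistent text and honest disclosure.

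**What to change.** 1. Reconcile the DSMB membership list, the *Unblinded Reporting* paragraph and the report descriptions in section 6.D with the blinding statement in section 4.
2. Either remove the PI and Co-PIs from DSMB membership, or confine them to open sessions with data pooled across arms. By-arm summaries and unblinded SAE material should go only to members confirmed to have no role in trial conduct. Four listed members remain, subject to that confirmation.
3. State how unblinded data reach an investigator when safety requires it: who decides, and who is told.
4. If by-arm or unblinded reports have already reached the PI or Co-PIs, say in the results paper which reports and when.

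The cost is a roster or charter edit, a clarifying sentence in section 6.D and, if needed, a disclosure sentence in the report. There are no added participants, visits or procedures.
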